- 1.2 18-month viral load will be assessed using blood draws taken during the 18-month assessment in the community (for microfinance group members) and at the facility (for non-microfinance group members).
- 2. For clinical secondary outcomes, we will measure systolic blood pressure and hemoglobin A1c at baseline and 18-months for all 900 microfinance group members enrolled in the trial. Blood pressure will be measured in the community by the clinical officer using a blood pressure arm cuff. HbA1c will be measured in the community by the clinical officers using a point of care test.
- 3. For non-clinical secondary outcomes, we will measure retention in care on an ongoing basis for all enrolled trial participants. Retention in care will be based on study records (REDCap) for intervention recipients and on medical records for facility care patients.
- 4. For exploratory outcomes and mediation analyses, we will collect survey data from all enrolled trial participants: at enrollment and 18-months for all trial participants, with an additional round of survey data collection at month 9 for all microfinance group members. Surveys will be administered by a research assistant to participants in a private location in-person. Surveys will assess demographics, health insurance enrollment and utilization, social support (Oslo Social Support Scale-3), quality of life (adapted version of the MOS-HIV scale), psychological distress (Patient Health Questionnaire-4), self-reported ART adherence (based on the adapted ACTG Adherence Questionnaire), self-reported adherence to NCD medications (based on the extent of DOSE-Nonadherence Questionnaire), barriers to accessing care, patient satisfaction with care, felt HIV stigma (9-item measure of felt stigma validated in Kenya). The survey instrument is included in Appendix III. For exploratory outcomes, we will collect data on microfinance group performance (e.g., saving and lending activities, loan default rates) for all microfinance group participants. Microfinance group performance data will be collected on a quarterly basis and recorded via REDCap. The microfinance data collection tool is included in Appendix IV.

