13	<pre>[relation_to_head] Show the field ONLY if: [house_head] = '2'</pre>	6. Relation to household head (Una uhusiano upi na kiongozi wa nyumba)	radio 1 Spouse (Mchumba) 2 Child (Mtoto) 3 Other (Mwengine)

14	<pre>[relation_to_head_spec ify] Show the field ONLY if:</pre>	6a. Other relation to household head, specify (Uhusiano mwingine usiotajwa, eleza)	text
	[relation_to_head] = '3'		
15	<pre>[respondent_demographi cs_complete]</pre>	Section Header: Form Status Complete?	dropdown 0 Incomplete 1 Unverified 2 Complete
Inst	rument: Health Insur	ance (health_insurance)	
16	<pre>[healthcare_decision s]</pre>	Section Header: I would like to ask you some questions about health insurance. Please answer honestly and to the best of your knowledge. All responses are confidential. (Ningependa kukuuliza maswali kadhaa kuhusu bima ya afya. Tafadhali jibu kwa uaminifu na kulingana na ufahamu wako. Majibu yote ni ya siri.) 1. Who makes the main decisions regarding healthcare for your household? For example where to seek healthcare, when to seek healthcare, etc (Je, ni nani katika nyumba yako hufanya maamuzi kuhusu mambo ya afya kama vile mahali na wakati wa kutafuta huduma ya afya)	radio 1 Self (Wewe mwenyewe) 2 Partner/Spouse (Mpenzi/Mchumba/Mume/Mke wako) 3 Other (Nyingine)
17	<pre>[other_decision_make r] Show the field ONLY if: [healthcare_decisions] = '3'</pre>	1a. Who else apart from the ones listed above makes the decisions regarding healthcare for your household, specify (Je, ni nani mwingine hufanya maamuzi kuhusu mambo ya afya kama vile mahali na wakati wa kutafuta huduma ya afya ambaye hajatajwa, eleza)	text
18	[enrolled_in_nhif]	2. Have you ever been enrolled in NHIF (National Hospital Insurance Fund) (Je, umewahi kusiajiliwa kwa bima ya NHIF (Bima ya Afya ya Kitaifa)	radio 1 Yes (Ndio) 2 No (La)
19	<pre>[nhif_first_enrolled] Show the field ONLY if: [enrolled_in_nhif] = '1'</pre>	2a. Do you remember when you were first enrolled in NHIF (Je unakumbuka ni lini ulijiandikisha kwa NHIF)	radio 1 Yes (Ndio) 2 No (La) 98 Don't know (Sijui)
20	<pre>[when_enrolled_in_nhi f] Show the field ONLY if: [nhif_first_enrolled] = '1'</pre>	2b. When were you enrolled in NHIF (Ni lini ulijiandikisha kwa NHIF)	text (date_dmy)
21	<pre>[nhif_super_cover] Show the field ONLY if: [nhif_first_enrolled] = '1'</pre>	2c. Do you currently have an NHIF cover (Je kwa sasa una bima ya Afya ya NHIF)	radio 1 Yes (Ndio) 2 No (La) 98 Don't know (Sijui)

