22	<pre>[remember_nhif_use] Show the field ONLY if: [nhif_super_cover] = '1'</pre>	2d. Do you remember the number of times you have used NHIF in the past 12 months (Unakumbuka ni mara ngapi umetumia NHIF kwa miezi 12 iliyopita)	radio 1 Yes (Ndio) 2 No (La) 98 Don't know (Sijui)

23	<pre>[times_used_nhif_pst12 mnths] Show the field ONLY if: [remember_nhif_use] = '1'</pre>	2e. How many times have you used NHIF to cover health expenses of your household members in the past 12 months (Je, ni mara ngapi umetumia NHIF kulipia gharama ya matibabu ya watu wa nyumba yako kwa miezi 12 iliyopita)	text
25	<pre>[reason_no_nhif_cove r] Show the field ONLY if: [nhif_super_cover] = '2' [no_nhif_cover_specif y] Show the field ONLY if: [reason_no_nhif_cover]</pre>	2f. Why don't you have NHIF coverage (Ni kwa nini hauna bima ya afya ya NHIF) 2g. Other reason for no NHIF coverage, specify (Sababu nyingine ya kutokuwa na bima ya NHIF, eleza)	radio 1 Lack of finances (Ukosefu wa fedha) 2 Unsure how to access NHIF (Sina uhakika jinsi ya kupata bima ya NHIF) 3 See no benefit (Sioni faida yake) 4 Other (Nyingine) text
26	= '4' [other_cover]	3. Are you currently covered by any other health insurance apart from NHIF (Je, kwa sasa una bima yoyote nyingine ya afya kando na NHIF)	radio 1 Yes (Ndio) 2 No (La) 98 Don't know (Sijui)
27	[other_cover_specify] Show the field ONLY if: [other_cover] = '1'	3a. Please indicate the health insurance cover (Tafadhali taja jina la bima hiyo)	text
28	<pre>[health_insurance_comp lete]</pre>	Section Header: Form Status Complete?	dropdown 0 Incomplete 1 Unverified 2 Complete
Inst	rument: OSLO Social S	Support Scale -3 (oslo_social_support_scale_3)	
29	<pre>[close_pple_yu_can_cou nt_on]</pre>	Section Header: I would like to know about the type of social support that is available to you. Please tell me how much you agree or disagree with the following statements. Sasa, ningependa kujua kuhusu msaada wa kijamii unaopatikana kwako. Tafadhali nieleze jinsi gani unavyokubali au kutokubaliana na maelezo yafuatayo. 1. How many people are so close to you that you can count on them if you have great personal problems	radio 1 None (Hakuna) 2 1-2 (Mmoja hadi wawili) 3 3-5 Watatu hadi watano) 4 5+ (Zaidi ya watano)
		(Je, ni watu wangapi wako na uhusiano wa karibu nawewe na unaweza wategemea ukiwa na shida yeyote ya kibinafsi)	

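### Current NHIF cover is asked only of respondents who remember when they first enrolled, so cover and use are missing for the rest of the ever-enrolled, and any cover rate depends on how those blanks are treated

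*Combined protocol and SAP*

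**What the plan says.** Section 7.1 (Data Collection), item 4, names "health insurance enrollment and utilization" among the survey domains collected for exploratory outcomes and mediation analyses. Microfinance members are surveyed at months 0, 9 and 18, and Arm C at months 0 and 18.

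The NHIF items in Appendix III run as follows:

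- Field 18, with no display rule printed: "2. Have you ever been enrolled in NHIF (National Hospital Insurance Fund".
- Field 19 (item 2a): "2a. Do you remember when you were first enrolled in NHIF", answered Yes (1), No (2) or Don't know (98). Its rule is "nhif_first_enrolled] Show the field ONLY if: [enrolled_in_nhif] = '1", so it goes to everyone ever enrolled.
- Field 20 (item 2b): the enrolment date, shown only if field 19 = 1.
- Field 21 (item 2c): "2c. Do you currently have an NHIF cover". Its rule is "nhif_super_cover] Show the field ONLY if: [nhif_first_enrolled] = '1".
- Field 22 (item 2d), on recall of NHIF use: "remember_nhif_use] Show the field ONLY if: [nhif_super_cover] = '1". Field 23 (item 2e), the number of uses, follows from field 22.
- Field 24 (item 2f), the reason for no cover: "Show the field ONLY if: [nhif_super_cover] = '2". Field 25 (item 2g) follows from field 24.
- Field 26 (item 3): any current insurance other than NHIF, with no display rule printed.

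The documents give no rule for coding a blank field 21 and no denominator for a cover rate.

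**The concern.** Fields 20 and 21 carry the same display rule. It suits field 20, because someone who cannot recall the date cannot supply it. It has no bearing on field 21, because a person can forget when they joined and still know whether they are insured today.

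As built, current cover and NHIF use are observed in a group defined by memory of a date. A respondent whose recall differs between waves can move from covered to blank, or back, with no change in cover. An analyst who reads a blank as no cover will under-count the insured. One who drops the blanks will describe people who remember dates.

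Insurance is not foreign to the study's rationale. Section 1.1 notes that most Kenyans are uninsured and pay for non-HIV care themselves, and section 6.1 charges patients for NCD medication. What is at stake is a correct exploratory description of cover and use.

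**Working it through.** **No plan figure to reproduce.** The documents state no NHIF cover rate, recall share or precision target for this item.

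**Skip logic, followed for an ever-enrolled respondent (field 18 = 1):**

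| Recalls date (field 19) | Insured today | Field 21 | Fields 22–23 (use) | Fields 24–25 (reason for no cover) |
|---|---|---|---|---|
| Yes | Yes | Yes | open | not shown |
| Yes | No | No | not shown | open |
| No or Don't know | Yes | blank | not shown | not shown |
| No or Don't know | No | blank | not shown | not shown |

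The last two rows are identical, so the form cannot separate insured from lapsed among those who do not recall the date. Field 26 cannot help, because it excludes NHIF. The affected records can still be told apart from the never-enrolled: they have field 18 = 1 and field 19 = 2 or 98.

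**Comparison within the same tool.** The farm-land items meet the same problem. The item on knowing the acreage opens only the acreage itself (field 146), while land use (field 147) depends on the parent item about renting or owning land. The NHIF block departs from that pattern, which points to a slip rather than a choice.

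**Effect on a cover rate.** Let e = share ever enrolled, r = share of those who recall the date, and cr and cf = current cover among those who do and do not recall it. All four are assumptions. The true rate is e[r·cr + (1−r)·cf].

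- (A) Blanks counted as uncovered, all respondents in the denominator: recorded e·r·cr. Error = −e(1−r)·cf, negative whenever any non-recaller is insured.
- (B) Blanks excluded, never-enrolled counted as uncovered: recorded B = e·r·cr / [1 − e(1−r)]. Error = e(1−r)·(B − cf), positive when cf is below B.
- (C) Rate among the ever-enrolled, using only those asked: recorded cr. Error = (1−r)(cr − cf), with the sign of cr − cf.

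With e = 50%, r = 70%, cr = 50%:

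| cf | True, all | (A) | (B) | True, ever-enrolled | (C) |
|---|---|---|---|---|---|
| 50% | 25.0% | 17.5% | 20.6% | 50% | 50% |
| 30% | 22.0% | 17.5% | 20.6% | 44% | 50% |
| 10% | 19.0% | 17.5% | 20.6% | 38% | 50% |

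First row: true = 0.5 × (0.35 + 0.15) = 0.25; A = 0.5 × 0.7 × 0.5 = 0.175; B = 0.175 / 0.85 = 0.206.

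**Wider range.** Take e = 30, 50, 70%; r = 50, 70, 90%; cr = 30, 50, 70%; cf = 10, 30, 50, 70%, which gives 108 combinations.

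| Handling | Too low | Equal | Too high | Error, points |
|---|---|---|---|---|
| (A) | 108 | 0 | 0 | −24.5 to −0.3 |
| (B) | 79 | 1 | 28 | −18.8 to +9.7 |
| (C) | 27 | 27 | 54 | −20 to +30 |

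These counts describe the assumed grid and are not probabilities.

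**Bounds that the collected data can give.** None of the non-recallers covered: e·r·cr. All covered: e·r·cr + e(1−r). With the values above, this is 17.5% to 17.5% + 15% = 32.5%. The width, e(1−r), is the share of respondents with field 18 = 1 and field 19 = 2 or 98, so one cross-tabulation shows how much this matters.

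**After re-gating.** If field 21 depended on field 18 = 1, every ever-enrolled respondent would be asked. The first row would then read 25.0%, apart from reporting error.

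**The case against.** The strongest case on the other side is that nothing planned depends on this item. Section 8.3 names household economics and access to care as the main mediators, then food security, social support and stigma; insurance is not among its named confounders. The outcome and dropout models in the addendum's revised analysis plan do not include NHIF, and the cost inputs in section 9 do not mention it. Ever-enrolment (field 18) is asked without a printed gate, so part of the insurance measure is intact. All of this stands and sets the severity. It does not remove the defect, because section 7.1 lists the measure and the form fails to collect part of it. The multiple imputation in the addendum covers missing baseline covariates in the viral-suppression analyses, not this item.

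A reader might go further and infer that NHIF cover is simply understated. If true cover were 20–40% and 20–60% of covered people forgot the date, the shortfall would be 4 points (0.2 × 0.2) to 24 points (0.4 × 0.6). The documents do not support that as a general conclusion. It follows only for a count of covered people, or a rate that takes blanks as uncovered, and the plan sets no such rule. With blanks treated as missing, the error can vanish or reverse, as (B) and (C) show. The inputs to that range are also assumed.

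**Conclusion.** The skip rule is an error on the face of the tool. Current NHIF cover, NHIF use and the reason for no cover are missing for every ever-enrolled respondent who does not recall when they enrolled. Two statements hold without a figure from outside the documents: the number recorded as covered is too low whenever any such person is insured, and the form cannot distinguish insured from lapsed in this group. The direction of error in a cover rate depends on how blanks are handled, and its size depends on recall and cover shares that the documents do not give. All point values above rest on assumed inputs.

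The effect is confined to the exploratory insurance measure. Viral suppression, retention, blood pressure and HbA1c are not touched. Minor.

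**What to change.** For any further use of the form, show field 21 when field 18 = 1, and keep the recall condition on field 20 alone. This is one branching edit in REDCap. The printed tool is dated July 2024 and the addendum already reports the primary analysis as done, so the edit may come too late for this trial.

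For surveys already collected:

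1. Code field 21 as missing, not as no cover, when field 18 = 1 and field 19 = 2 or 98.
2. Report the number of such records by arm and wave.
3. Report current cover with two bounds: all of these records covered, and none covered.
4. Do not carry cover from one wave to another. Cover can start or lapse between surveys, and Arm C has no month-9 survey, so carrying values would trade missing data for possible misclassification, unevenly across arms.

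The cost is one recode, one cross-tabulation and two extra rows in the exploratory tables. The drawback is that the reported cover figure becomes a range.

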For **qualitative mediation analyses**, we will conduct qualitative in-depth with 40 participants from the Aim 1 randomized controlled trial (n=20 from the MF+ICB arm and =20 from the MF+SOC arm). Following the Aim 1 trial's 18-month assessment, research assistants will provide information to a purposively selected sample of n=40 participants and invite them to join the qualitative data collection. Following the Aim 1 trial's 18-month assessment, research assistants will also invite n=10 current AMPATH staff who delivered the intervention to participate in in-depth interviews. Individuals who are interested in participating in the Aim 2 interviews will complete the informed consent form in Appendix V.

- 8.1.1 Inclusion criteria for trial participants:
 - consented to participate in the intervention study (Aim 1) and completed at least the baseline and 18-month assessment;
 - participated in at least 2 MF group meetings during the study period; and
 - able and willing to provide informed consent for the qualitative study.
- 8.1.2 Inclusion criteria for key stakeholder and care providers:
 - Delivered care in the intervention arm of the trial for at least 6 months;
 - 18 years of age or older; and
 - Able and willing to provide informed consent to participate.

Data for all Aim 1 participants (n=900 microfinance groups + 300 SOC) collected via the survey measures (Appendix III) administered at baseline, 9-month, and 18-month follow-up visits will be used for the Aim 2 quantitative mediation analyses.

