8.3 Aim 2 statistical analyses

Quantitative mediation analyses. We will use causal mediation analysis to evaluate the importance of causal pathways between microfinance and integrated community-based care and viral suppression and retention. We will use the data described in Aim 1 collected at baseline, 9-month, and 18-month follow-up visits. The primary analysis will focus on two main mediators: household economic conditions and access to care. We will estimate the mediation effect of each mediator separately using the difference method and account for multiple comparisons using a Bonferroni correction. The generalized linear models needed to implement the difference method will adjust for key confounders such as education, location, gender, and age. We will perform a sensitivity analysis of the assumption of no unmeasured mediator-outcome confounders. As a secondary analysis, we will use causal mediation analysis to evaluate the mediation effect of food security, social support, and HIV-related stigma. We hypothesize that there will be similar improvements in household economic conditions between the two MF and MF+ICB groups, but that barriers in access to care will be more improved in the MF+ICB arm. Differences in these mechanisms will provide important information regarding the additive impact of integrated community-based care on the hypothesized relationships.

Qualitative mediation analyses. Text from the n=50 interviews will be coded into a hierarchical, branching structure in which broad concepts are first identified, along the domains identified in the interview guides and our conceptual model, and then themes and variations within those themes will be defined and text will be labeled according to these definitions. Coded data from intervention participants will be compared to identify mechanisms through which MF and community-based care impacted retention in HIV care and adherence to ART, and the additive impact of the community-based care delivery in the intervention group. Specifically, data will compare between the intervention arms the added benefits of community-based care, beyond those relevant to both groups from the MF activities. We will triangulate findings using data from the qualitative study to explain and expand on findings from the quantitative mediation analysis.

9. Aim 3. Cost-effectiveness analysis

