144	[own_or_rent_farm_land]	18. Do you rent or own any farm land (Je unakodisha au unamiliki shamba lolote)	yesno 1 Yes 0 No Custom alignment: RH
145	<pre>[know_acres_owned_by_h h]</pre>	18a. Do you know the number of acres of agricultural land owned by household	radio

	Show the field ONLY if:	(Unajua kiasi ya shamba unayomiliki)	1 Yes
	[own_or_rent_farm_lan d] = '1'		2 No
			3 Don't know
			Custom alignment: RH
146	[acres_of_land_owned]	18b. If yes, how many acres of agricultural land does your household own	text
	Show the field ONLY if: [know_acres_owned_by _hh] = '1'	(lkiwa ndio, ni hecta ngapi ya shamba ya kilimo ambayo nyumba yako inamiliki)	
147		19. What is the land used for	checkbox
	d_land] Show the field ONLY if: [own_or_rent_farm_lan d] = '1'	(Je shamba hili latumika kivipi)	1 use_of_rented_or_owned_land1 Rer land incompleted la
			2 use_of_rented_or_owned_land2 Plan for how con (Ku mir ajili ya r
			3 use_of_rented_or_owned_land3 Pla for ger (Ku mir ajili kuz ma
			4 use_of_rented_or_owned_land4 Ani fari (Ufi wai
			5 use_of_rented_or_owned_land5 Lan sitt (Sh. kut
			6 use_of_rented_or_owned_land6 Oth (Ny
148	[other_use_for_land]	19a. If other use for land, specify	text
	Show the field ONLY if: [use_of_rented_or_own ed_land(6)]= '1'		
149	[household_economic_st	Section Header: Form Status	dropdown
	i —	I	

ı		1							
			1	Unverified					
			2	Complete					
Instr	Instrument: Employment and Income Status (employment_and_income_status)								
150	[primary_employment]	current employment and income status. (Kwa kumalizia ningependa kukuuliza kuhusu hali yako ya sasa ya kuajiriwa na mapato yako ya sasa hivi.) 1. Which of the following options best describes your primary employment? You are a (Je ni gani baadhi ya majibu yafuatayo inaeleza	dropdown						
	ningependa kukuuliza kuhusu hali yako ya sasa ya kuajiriwa na mapato yako ya sasa hivi.) 1. Which of the following options best describes your primary employment? You are a		1	1. Farmer (Mkulima)					
			2	2. Daily laborer/piece work earner in agricultural or health sector (Mfanyikazi wa kila siku katika sector ya ukulima ama afya)					
		3	3. Wage earner in non-agriculture large business (factory operation) (Mfanyi kibarua katika biashara kubwa isiyo ya kilimo (uendeshaji wa kiwanda))						
		mapato ya nyumbani kwako)	4	4. Small business owner (duka, kiosk, trade in farm produce) (Mfanya biashara ndogo (Duka, Kiosk, Kuuza bidhaa ya shamba))					

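### The farm-size question asks for acres in English and hectares in Swahili, and the form records neither the unit nor the language of each answer (minor)

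*Combined protocol and SAP*

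**What the plan says.** Item 146 is in the Household Economic Status instrument of Appendix III. The English prompt is "how many acres of agricultural land does your household own" and the Swahili prompt printed beside it is "ni hecta ngapi ya shamba ya kilimo ambayo nyumba yako inamiliki". *Hecta* is the hectare. The answer is stored in one field, "acres_of_land_owned", of plain text type. No unit field, range check or conversion rule is shown.

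The item opens only after a yes to item 145. In English that item reads "18a. Do you know the number of acres of agricultural land owned by household". Its Swahili form, "Unajua kiasi ya shamba unayomiliki", asks only about the amount of land and names no unit.

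The metadata form (items 1 to 6) records study ID, group ID, date, interviewer, start time and form status. It does not record the language of interview. Section 7.1 says "Surveys will be administered by a research assistant to participants in a private location in-person", also without stating the language. Section 10.1.2 provides for back-translation of consent documents. No such step is stated for the survey.

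On use of the data, section 8.1 says that the Appendix III survey measures "will be used for the Aim 2 quantitative mediation analyses", and section 8.3 says "The primary analysis will focus on two main mediators: household economic conditions and access to care". Neither section says how household economic conditions is scored or which items enter it.

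**The concern.** The two prompts ask for the same quantity in different units and share one storage field. A research assistant reading the Swahili literally and another reading the English could enter different numbers for the same farm. Because language and unit are not recorded by design, the structured data alone would not show which values to convert.

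Item 146 is the only measure of land size in the instrument that bears on one of the two main mediators. If it enters the mediator score as a number, unit error adds noise to the mediator, and noise of this kind usually weakens an estimated mediated effect. The survey is given at 0, 9 and 18 months to microfinance members and at 0 and 18 months to Arm C. A household whose unit changed between rounds would therefore show a change in land that did not happen.

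**Working it through.** The plan states no figure on this point, so there is nothing to reproduce. The check is a unit conversion, followed by illustrations under stated assumptions.

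**Unit ratio.** 10,000 m² per hectare ÷ 4,046.856 m² per acre = 2.471 acres per hectare. A hectare answer read as acres is 1/2.471 = 0.405 of the true acreage.

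**False change between rounds for one household.** Hectares first and acres later: 2.471 − 1 = a 147% apparent rise. Acres first and hectares later: 1 − 0.405 = a 60% apparent fall (rounded).

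**Effect on the recorded distribution.** Let f be the share of answers given in hectares but read as acres, unrelated to farm size. The documents do not give f, so a range is shown.
- Recorded mean ÷ true mean = (1 − f) + f/2.471
- Added SD on the log scale = ln(2.471) × √(f(1 − f)), with ln(2.471) = 0.905

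| f | recorded/true mean | added log SD |
|---|---|---|
| 0 | 1.00 | 0 |
| 0.10 | 0.94 | 0.27 |
| 0.25 | 0.85 | 0.39 |
| 0.50 | 0.70 | 0.45 |
| 0.75 | 0.55 | 0.39 |
| 1 | 0.405 | 0 |

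At f = 0 there is no error. At f = 1 every value is off by the same factor and nothing is mixed.

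**Reliability of this one item.** Assume a true log-scale SD s between 0.6 and 1.0 (not in the documents). Reliability = s²/(s² + f(1 − f) × 0.818), where 0.818 = ln(2.471)².
- f = 0.10: 0.36/(0.36 + 0.074) = 0.83 at s = 0.6, and 1/(1 + 0.074) = 0.93 at s = 1.0.
- f = 0.30: 0.36/(0.36 + 0.172) = 0.68, and 1/(1 + 0.172) = 0.85.
- f = 0.50: 0.36/(0.36 + 0.205) = 0.64, and 1/(1 + 0.205) = 0.83.

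**From the item to an index.** These reliabilities describe log land area, not the mediator. Suppose the mediator were an index of 21 equally weighted, standardised, uncorrelated components: the 15 household items, the 5 named livestock counts and land. Even the worst item reliability above, 0.64, would then lower the index reliability only to about 1 − 0.36/21 = 0.98. Other weights would change this.

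**The case against.** The strongest reply is that harm has not been shown. The field name and both English labels say acres and are printed next to the Swahili, and a research assistant fills in the form. Staff may have recorded acres throughout. The field takes free text, so a unit could have been typed with some answers. Nothing says that land area enters the mediator, and the same survey collects household assets, livestock, employment and income. All of this stands. It limits the point to what the instrument permits, not what happened.

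Three stronger readings are tempting, and the documents do not support them.

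- *The mediator is contaminated.* That would need land area in the score and some answers in each unit. The documents establish neither.
- *The error follows county or arm.* Interviewer codes fall into two sets, HBR and HTR, and a reader might take these for county teams that favour different wording. The documents do not say so. The summary states that randomization is stratified by county, and section 8.3 adjusts the mediation models for location. Addendum item 8 moved about 30 of the 300 Arm C matches across counties, and that arm is not randomized.
- *The trial's main result is at risk.* The revised analysis plan in addendum item 10 lists the covariates of the dropout and outcome models, and land area is not among them. The revised retention definition in item 11 does not involve it either.

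What the reply does not remove is the conflict itself. A field named for acres cannot be read with confidence while its Swahili prompt asks for hectares, and the documents show no step that would have caught or resolved this.

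**Conclusion.** The instrument is wrong as written: item 146 has two units, one field, and no record of unit or language for each answer. The possible error is a factor of 2.47 for any one answer. Whether it matters depends on two facts the documents do not give: whether land area is part of the household economic mediator, and which units were recorded. If land area is used and both units occur, the item loses reliability, to somewhere between 0.64 and 0.93 under the assumptions above (f from 0.10 to 0.50, s from 0.6 to 1.0, random mixing). The loss for a many-item index would be much smaller. Uniform hectare answers would give a constant mislabelling, and uniform acre answers no error. The primary and secondary viral-suppression analyses are unaffected. Severity is minor.

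**What to change.** For any further use of the form, reconcile the two prompts of item 146 to one unit, acres, and name that unit in the Swahili of item 145 as well.

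The addendum describes follow-up and analysis in the past tense, so the collected data need a separate step. Ask the field teams which unit they recorded, inspect the raw text entries for typed units, and document the answer. State in section 8.3 whether land area enters the household economic mediator and how that mediator is scored.

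Unless the unit is confirmed, leave the item 146 number out of the measure and use item 144 (rents or owns farm land, yes/no) with the asset and livestock items. If acreage is used at all, restrict it to records whose unit is confirmed. Limiting the analysis to households whose values agree across rounds to within a factor of 2.47 would not serve. It would keep households that switched units and those that always answered in hectares.

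The cost is one translation change, a short query to field staff and, at most, one dropped component. The loss is some detail on wealth, because item 144 carries no size and does not separate renting from owning.
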